Rationale. Our preliminary data in mice suggest that RE enhances adipocyte catecholamine sensitivity through a novel mechanism involving the delivery of muscle-specific miR-1 to adipose via exosomes. The in vitro analyses in Aim 1 will explore this process mechanistically, with Aim 2 extending the analyses to primary human myotubes and adipocytes. The purpose of this aim is to determine if our working model translates to humans *in vivo*. Analyses of serum exosomes, muscle and adipose tissue isolated before and after a bout of RE will determine if miR-1 potentially mediates muscle-adipose crosstalk during exercise in humans. The ability of isolated exosomes to induce adipocyte lipolysis *in vitro* by enhancing catecholamine sensitivity through CEBP α activation of β AR-3 expression will be assessed.

Design. Relatively sedentary, generally healthy lean (BMI <25) and obese (BMI >30) men and women between 18-30 years of age without study contraindications will be recruited (see inclusion/exclusion criteria in Human Subjects section). Potential eligibility will be assessed by self-reported height and weight, and by reporting no participation in regular (>1 day per week) exercise for at least the past three months. All potential participants will arrive fasted to the Center for Clinical and Translational Sciences (CCTS). After giving written, informed consent, a detailed medical history form will be filled out to screen for eligibility. Measures of physical activity level will be collected before baseline blood, adipose, and muscle samples are taken. We intend to recruit an equal number of lean and obese participants (n=40 in each group, 20 men and 20 women). Power analysis based on the change we observed in miR-1 abundance in exosomes following a bout of knee extensions in a pilot study of 10 individuals, indicated that n=36 is required in each group. We are requesting n=40 in both the lean and obese groups based on an expected difference in means between 1 and 1.95 and an expected standard deviation of 0.45, with the power set at 0.8 and alpha at 0.05. This will accommodate 10% drop out prior to completing all biopsies.

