Following a brief rest period, subjects will perform two lower body RE tasks to failure (knee extension and leg press) with blood samples drawn pre- and immediately, 30, 60 and 90 minutes post-exercise. Biopsies of the vastus lateralis and abdominal subcutaneous adipose tissue will be obtained pre- and post-exercise (at approximately 60 and 90 min post, respectively; see graphic abstract in the Human Subjects section).

Experiment 3.1. Exosomal, muscle, and adipose miR-1 abundance will be quantified, as well as miR-1A/B primary transcripts in muscle and adipose by qPCR as described in the SOP section.

Experiment 3.2. Isolated exosomes from the 30 and 60 minute time points will be applied to differentiated ADHASC for 24 hr, and lipolysis *in vitro* and the β AR-3 pathway gene expression assessed as described in the SOP section. Pre-RE exosomes will be transfected with miR-1 mimic (Pre-plus) and 30 minute post-RE exosomes with anti-miR-1 oligonucleotide (Post-minus) and compared to mock transfected exosomes from those time points. These modified exosomes will be incubated with differentiated adipocytes to parallel Aim 1 mouse Experiments 1.1 and 1.2.

Methods.

Resistance exercise (RE). Following determination of each subject's one repetition max (1-RM, see Human Subjects section for detailed description), subjects will perform two exercises, knee extension and leg press at 80% of 1-RM, designed to work the quadriceps. Subjects will perform three sets of eight repetitions, with a 90-120 second rest between sets, with a fourth set performed to failure. RE will be performed on pneumatic resistance devices (Keiser Sports Health Equipment, Fresno, CA).

Muscle biopsy. A muscle biopsy will be obtained from the vastus lateralis at baseline and approximately 1 hr post-exercise under local anesthetic (1% Xylocaine HCl, 3cc). A 1/4 inch wide incision will be made and a sterile 5mm Berkstrom biopsy needle (Pelomi Industries, Denmark) inserted with suction to obtain a 100-200 mg muscle sample. [name], study physician and co-investigator on this project, has extensive experience with this procedure. It is well-tolerated and volunteers routinely provide multiple samples^{83,89,94-96}. Muscle is snap frozen in liquid nitrogen and stored at -80°C until RNA isolation.

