Adipose Biopsy. An abdominal subcutaneous fat biopsy sample will be obtained from the lower abdominal wall prior to and approximately 90 min post exercise. The adipose biopsy procedure is similar to the thigh muscle biopsy procedure, except that 1-2 g of adipose tissue is routinely obtained^{42,79,94,97,98}.

Human serum analyses. Glucose and insulin will be measured in the University of Kentucky CCTS Biochemical Analysis Laboratory^{99,100} from baseline serum collected from fasting lean and obese participants

to calculate HOMA-IR (Glucose*Insulin/405) as a measure of muscle insulin sensitivity. NEFA and free glycerol will be measured ⁸¹ both at baseline and in serum collected at multiple time points following the resistance exercise bout, and used to calculate a simplified “anti-lipolytic index” (NEFA*Insulin), which indicates adipocyte insulin sensitivity based on insulin’s ability to suppress lipolysis ¹⁰¹. In humans, fasting serum norepinephrine is positively associated with isoproterenol ED₅₀ in isolated adipocytes. Thus, elevated fasting catecholamines may be indicative of decreased adipose tissue catecholamine sensitivity ¹⁰². We will also measure serum epinephrine and norepinephrine by HPLC (Vanderbilt University Hormone & Analytical Services Core) ¹⁰³.

Statistical Analysis. The College of Health Sciences supports the effort of a biostatistician through the Office of Research to provide dedicated support to funded investigators. A one-way repeated measures ANCOVA adjusting by sex will be used to determine if a significant difference exists between the groups in response to RE for miR-1 and miR-1A/B primary transcripts. If a significant difference is detected, LSD *post-hoc* comparisons will be performed to identify the source of significance with $p \leq .05$. The Pearson correlation coefficient will be used to determine whether muscle, serum, and adipose miR-1 and miR-1A/B primary transcripts are correlated to tissue insulin sensitivity and fasting catecholamines at baseline. All statistical analyses will be performed using SAS[®] 9.4 (SAS institute, Cary NC).

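### Aim 3 names a repeated measures ANCOVA with no missing-data rule; in its classical form it would discard the pre, 0 and 30 min blood values of anyone missing a later draw, whereas a mixed model would keep them

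*Combined protocol and SAP*

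**What the plan says.** Specific Aim 3, Design, bases the sample size on "the change we observed in miR-1 abundance in exosomes following a bout of knee extensions in a pilot study of 10 individuals", which is a blood measure. The power analysis "indicated that n=36 is required in each group", and 40 lean and 40 obese participants are to be recruited. The margin between the two figures is explained by one sentence: "This will accommodate 10% drop out prior to completing all biopsies".

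The same section has "blood samples drawn pre- and immediately, 30, 60 and 90 minutes post-exercise". The post-exercise muscle biopsy follows at about 60 min and the adipose biopsy at about 90 min. Under Expected outcomes and alternative approaches, the pilot is said to have shown the highest exosomal miR-1 at 30 min, with a decline starting by one hour.

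Specific Aim 3, Statistical Analysis, says "A one-way repeated measures ANCOVA adjusting by sex will be used" to compare the groups' response to exercise. SAS 9.4 is named, but no procedure. The supplied text gives no analysis set and no rule for missing values.

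**The concern.** The plan expects some participants to leave during a session in which the most informative blood sample comes before both post-exercise biopsies. Someone who leaves at about 60 min can already have given the pre, 0 and 30 min draws. A classical repeated measures analysis, for example PROC GLM with a REPEATED statement, needs all five blood values and drops that person entirely. The lean-obese comparison at the expected peak would then lose people whose peak value had been measured.

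Two things are at stake. The first is some precision. The second is selection: if leaving is related to the response, and more so in one group than in the other, an analysis of complete rows compares selected subsets of the two groups.

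**Working it through.** **Inputs from Specific Aim 3, Design.** Required 36 per group, recruited 40, drop-out 10%, difference 0.95 (means of 1 and 1.95), SD 0.45, power 0.80, alpha 0.05 (taken as two-sided), five blood times.

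**1. The drop-out step reproduces.** 36 / (1 − 0.10) = 40, and 40 × 0.90 = 36.

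**2. The 36 does not follow from the inputs as labelled.** n per group = 2 × (1.960 + 0.842)² × 0.45² / 0.95² = 3.5, so 4 (5 with the t distribution). If 0.45 were the standard error from the pilot of 10, the SD would be 0.45 × √10 = 1.42 and the same formula would give 36. That reading is an inference and a separate matter. For the power figures here I use the standardised effect at which 36 per group gives 80% power, d = 0.67. With the labelled inputs, d = 0.95 / 0.45 = 2.11 and power exceeds 0.999 at both 36 and 40.

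**3. Who is affected.**

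| Participant | Blood row | Classical ANCOVA, blood only | Mixed model |
|---|---|---|---|
| Declines a biopsy, gives all five draws | complete | kept | kept |
| Leaves after the 30 min draw | pre, 0, 30 | dropped | three values kept |
| Leaves before exercise | pre at most | dropped | no peak value to use |

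Only the second row makes a difference at the peak.

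**4. Precision at 30 min.** Treat the pre-to-30 min change as the quantity compared.
- All 10% leave after 30 min: 40 per group have the change, 36 have complete rows. SE ratio = √(40/36) = 1.054. Power at d = 0.67 is 0.84 against 0.80.
- Half of the 10% leave after 30 min and half before exercise: 38 against 36. SE ratio = √(38/36) = 1.027. Power is 0.82 against 0.80.

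**5. Adding failed draws.** The documents give no rate, so the rates below are assumptions, with all 10% leaving after 30 min. Complete rows = 40 × 0.90 × (1 − u)⁵. Participants with both pre and 30 min values = 40 × (1 − u)².

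| Unusable per draw, u | Complete rows | Pre and 30 min pairs | SE ratio | Power, complete rows / pairs |
|---|---|---|---|---|
| 0 | 36.0 | 40.0 | 1.05 | 0.80 / 0.84 |
| 1% | 34.2 | 39.2 | 1.07 | 0.78 / 0.83 |
| 3% | 30.9 | 37.6 | 1.10 | 0.74 / 0.82 |
| 5% | 27.9 | 36.1 | 1.14 | 0.69 / 0.80 |

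**6. Selection.** Suppose 10% leave in one group only, by a logistic rule in which the odds of leaving double per SD of the 30 min response. The complete-row mean of that group shifts by −0.066 SD, about a tenth of d = 0.67. Removing its top 10% outright shifts the mean by −0.195 SD, which is an extreme bound. A likelihood analysis that includes the 30 min value allows for leaving that depends on that value.

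**The case against.** A reader might infer that Aim 3 counts anyone who misses a biopsy as a drop-out and removes them from the blood endpoint. The documents do not support this. The sentence is a sample-size allowance and defines no analysis set. Exosomal, muscle and adipose miR-1 are listed as separate measurements, and nothing says that they must share one row. Setting the allowance by the specimens hardest to complete is, if anything, cautious for blood.

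A reader might also infer that the blood comparison will fall to about 31 of 40 per group. That figure needs an assumed 3% failure rate per draw, unconnected with biopsies, and every leaver going just after 30 min. Without failed draws, 36 remain, exactly the number that the plan requires.

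Three further points stand. The plan does not commit to the classical form, and its biostatistician might fit a mixed model anyway. The text refers to a Human Subjects section that is not in the supplied document and might hold rules on incomplete visits. Nothing suggests that leaving depends on circulating miR-1, which participants cannot feel, and the muscle biopsy is described as well tolerated.

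These points limit the size of the concern. They do not supply a missing-data rule or a procedure, and the method as named has a common form that discards measured peak values.

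**Conclusion.** The concern holds as a modest, cheaply corrected weakness in the analysis method. The plan expects incomplete participation, places its key blood sample before the post-exercise biopsies, and names a method that in its classical form would waste that sample for late leavers.

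The cost is at most about 5% in standard error and 4 points of power (0.80 against 0.84) at 10% drop-out with no failed draws. It is less if some leave before exercise and more if draws also fail. These power figures rest on d = 0.67, the effect implied by 36 per group. On the labelled difference and SD, power would be ample either way. Selection bias is possible but not shown; it requires leaving to be related to the response, and it distorts the comparison mainly when that relation or the amount of leaving differs between lean and obese participants.

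**What to change.** In Specific Aim 3, Statistical Analysis, replace the repeated measures ANCOVA with a likelihood-based mixed model, and state that:

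- it is fitted in SAS PROC MIXED with group, time, group-by-time and sex, and for blood with an unstructured covariance over the five times, the pre-exercise value being one of them;
- blood, muscle and adipose are modelled separately, each using every participant with available data for that specimen, whether or not all biopsies were completed;
- missing values are assumed missing at random given the observed values;
- biopsy completion is reported for the lean and obese groups.

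This takes a few sentences, uses software already planned and adds no participants. The price is reliance on missing-at-random, which cannot be verified from the data. It is a weaker assumption than complete-row analysis generally needs, so nothing is given up by the change.

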We expect that lean individuals will be more insulin sensitive than obese individuals, and that obese participants will display higher fasting NEFA in the context of higher fasting insulin (due to decreased adipose tissue insulin sensitivity). Including both lean and obese individuals will determine if adiposity affects the miR-1 acute response to RE. It is possible that release of miR-1 in exosomes from muscle will be lost or blunted in the obese cohort. However, we hypothesize that insulin sensitivity (assessed by HOMA-IR and the anti-lipolytic index) will be positively correlated to the serum miR-1 excursion following the RE bout in both populations. NEFA and glycerol will be measured both pre- and post-RE to determine whether changes in NEFA and glycerol from baseline are correlated with change in miR-1 in serum and/or adipose from baseline. We will also determine if the induction of adipocyte lipolysis *in vitro* is different in exosomes isolated from lean compared to obese participants following RE. Further, the *in vitro* studies will provide the opportunity to explore additional aspects of adipocyte metabolism that may be regulated by miRs, which will be informed by results of Aims 1 and 2. Overall, we expect results from this study to inform the design of a resistance exercise training trial in obese individuals. Moreover, the proposed studies are expected to provide the fundamental knowledge necessary to determine if exosomal miR-1 delivery to adipose tissue has the potential to form the basis for the development of a novel therapeutic strategy to treat obesity, particularly in individuals physically unable to exercise.

Table 1 provides our projected timeline for the proposed experiments. As discussed above, the preliminary data presented demonstrate that we have the necessary expertise to perform the proposed experiments so we do not anticipate any major delays; however, the experiments have been laid out to accommodate unforeseen delays such that the proposed experiments and analyses will be completed by the end of Year 5.

Table 1. Timetable for proposed experiments.

Specific Aim	Year 1	Year 2	Year 3	Year 4	Year 5
Aim 1: Determine if exercise-induced exosomal miR-1 enhances adipocyte adrenergic signaling through activation of β 3-AR expression.	breed, mature mice to 4 mo., perform Exp 1.1 analyze data	perform Exp 1.3 analyze data	breed, mature mice to 4 mo., perform Exp 1.4 analyze data	write manuscript	

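### HOMA-IR is labelled a muscle measure but has no muscle-specific term and shares its insulin value with the adipose index, so an insulin-driven miR-1 correlation cannot be assigned to either tissue

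*Combined protocol and SAP*

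**What the plan says.** Under Specific Aim 3, Human serum analyses, glucose and insulin are measured "from baseline serum collected from fasting lean and obese participants" and used "to calculate HOMA-IR (Glucose*Insulin/405) as a measure of muscle insulin sensitivity". NEFA and free glycerol are measured "both at baseline and in serum collected at multiple time points following the resistance exercise bout". NEFA is multiplied by insulin to give a simplified anti-lipolytic index, described as "NEFA*Insulin), which indicates adipocyte insulin sensitivity based on" insulin's suppression of lipolysis. Insulin is listed from baseline serum only. The two baseline indices therefore use the same insulin measurement, and any post-exercise version of the adipose index would have to reuse it.

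Under Specific Aim 3, Statistical Analysis: "The Pearson correlation coefficient will be used to determine whether muscle, serum, and adipose miR-1" and the primary transcripts "are correlated to tissue insulin sensitivity and fasting catecholamines at baseline". No log transformation, adjustment for insulin, component-wise analysis or comparison of the two correlations is described.

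Under Expected outcomes and alternative approaches, both indices serve one hypothesis: "insulin sensitivity (assessed by HOMA-IR and the anti-lipolytic index) will be positively correlated to the serum miR-1 excursion following the RE bout". There they stand together as insulin sensitivity, with no split by tissue.

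**The concern.** The plan gives one index a muscle label and the other an adipocyte label, then refers to tissue insulin sensitivity as the target of the correlations. Neither input to HOMA-IR is measured in muscle, and Aim 3 lists no insulin-stimulated test that could supply a muscle reading. Because insulin is a factor in both products, a single association between miR-1 and fasting insulin can produce two significant correlations. Under the plan's labels these could be taken as agreement between two tissues.

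Aim 3 asks whether miR-1 may mediate muscle-adipose crosstalk, so a muscle or adipose reading of these correlations would bear on its story. The direction of the two scales is a separate question: correcting the sign would not make either index more tissue-specific.

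**Working it through.** The plan states no correlation between the indices, no target r and no power for these correlations, so there is no figure to reproduce.

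**Inputs.** From the documents: HOMA-IR = Glucose*Insulin/405; adipose index = NEFA*Insulin; 40 lean + 40 obese = 80 participants. Assumed, because the documents give none: log-scale SDs of 0.06-0.10 for glucose (sG), 0.4-0.6 for insulin (sI) and 0.35-0.5 for NEFA (sN), with the three components independent.

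**Formulas (log scale).** The constant 405 drops out.
- Insulin's share of log HOMA-IR variance: sI²/(sI² + sG²)
- Insulin's share of log NEFA*Insulin variance: sI²/(sI² + sN²)
- Correlation of the two indices: sI²/√[(sI² + sG²)(sI² + sN²)]

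**Results over the assumed ranges.**
- HOMA-IR share: 0.16/(0.16 + 0.01) = 94%, up to 0.36/(0.36 + 0.0036) = 99%.
- NEFA*Insulin share: 0.16/(0.16 + 0.25) = 39%, up to 0.36/(0.36 + 0.1225) = 75%.
- Correlation, lowest: 0.16/√(0.17 × 0.41) = 0.61. Highest: 0.36/√(0.3636 × 0.4825) = 0.86.

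**Wider assumptions** (sI 0.30-0.60, sG 0.06-0.15, sN 0.25-0.50):
- Lowest: 0.09/√(0.1125 × 0.34) = 0.46.
- Highest: 0.36/√(0.3636 × 0.4225) = 0.92.
- Central SDs (sI 0.45, sG 0.10, sN 0.35): 0.2025/√(0.2125 × 0.325) = 0.77.

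**Raw scale.** The plan does not mention logs. For lognormal components at the central SDs, the raw-scale correlation is (e^0.2025 − 1)/√[(e^0.2125 − 1)(e^0.325 − 1)] = 0.2245/√(0.2368 × 0.3840) = 0.74. The choice of scale changes little.

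**What the planned correlations would show.** Simulation with raw-scale Pearson correlations, n = 80, central SDs and 4000 replicates; miR-1 is tied to one component only, at r = 0.4. Separation was judged with a Williams test for dependent correlations, which is not in the plan.

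| miR-1 tied to | Mean r, HOMA-IR | Mean r, NEFA*Insulin | HOMA-IR significant | NEFA*Insulin significant | Both significant | Williams test separates |
|---|---|---|---|---|---|---|
| Insulin | 0.37 | 0.29 | 93% | 76% | 75% | 17% |
| NEFA | 0.00 | 0.22 | 5% | 53% | 2% | 83% |
| Glucose | 0.08 | 0.00 | 11% | 4% | 2% | 17% |

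In the insulin row, HOMA-IR is significant alone in 93 − 75 = 18% of simulated trials, a result that the plan's label would describe as muscle. Across the four SD settings tried at n = 80, an insulin-only association made both indices significant in 38-81% of trials and was separated in 14-28%. A NEFA-only association was separated in 79-83%. At n = 40 (one BMI group) and central SDs, separation of a NEFA-only association falls to 54%.

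**Independence.** The plan expects that "obese participants will display higher fasting NEFA in the context of higher fasting insulin". A positive covariance c between log NEFA and log insulin, with their variances held fixed, replaces the numerator sI² by sI² + c and the term sI² + sN² by sI² + sN² + 2c. The ratio rises with c, so pooling lean and obese participants would push the overlap above these figures.

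**The case against.** The strongest reply is that the plan never commits to the contrast being criticised. It does not pair muscle miR-1 with HOMA-IR or adipose miR-1 with NEFA*Insulin, it does not define tissue insulin sensitivity, and its one stated hypothesis uses both indices together. A reader might infer that a muscle-versus-adipose comparison is planned; the text does not say so. That limits the stake to interpretation, but the muscle label is explicit and has no support in the formula.

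Three stronger readings are tempting and are not supported.
- **That the correlations cannot be read at all.** A NEFA-driven association leaves HOMA-IR near zero and is usually separable at n = 80. Only an association that runs through insulin is unassignable.
- **That the two are mostly one correlation counted twice.** At insulin and NEFA log SDs of 0.4 and 0.5, insulin supplies only 39% of log NEFA*Insulin variance. An index correlation of 0.61 means 37% shared variance (0.61²).
- **That fasting HOMA-IR chiefly reflects some other named organ.** The documents do not settle which tissue it reflects. They show only that the formula has no muscle-specific term.

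The adipose interpretation also does not rest on NEFA*Insulin alone. The plan correlates changes in NEFA and glycerol with change in miR-1, and Experiment 3.2 tests lipolysis in adipocytes directly. This stands, although it does not repair the baseline correlations. All three components are measured, so the problem can be corrected at analysis.

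**Conclusion.** The point holds in a limited form. As planned, the two indices cannot support a muscle-versus-adipose contrast when the miR-1 association runs through insulin, and the description of HOMA-IR as a muscle measure is unsupported by its formula. The label and the shared insulin term follow from the documents alone. The size of the overlap does not: 0.61-0.86, or 0.46-0.92 more widely, rests on assumed SDs and independent components. This is a secondary baseline analysis. It should be corrected because it changes what may be concluded from the correlations, but it has no bearing on the repeated-measures ANCOVA.

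**What to change.** - In Human serum analyses, describe HOMA-IR as a fasting whole-body index of insulin resistance.
- In Statistical Analysis, remove the word tissue from the correlation sentence and state that no muscle-versus-adipose contrast will be drawn from the two indices.
- Beside the index correlations, report the associations of each miR-1 measure with log insulin, log glucose and log NEFA as separate terms, adjusted for BMI group and sex.

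The component models should be a supporting analysis, not a pass/fail rule for an adipose claim. The plan expects NEFA and insulin to rise together in obesity, so requiring NEFA to contribute beyond insulin could discard real adipose signal.

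**Cost.** No new samples, visits or assays are needed, because all three components are already measured at baseline. The muscle-specific claim is given up, and a few secondary models are added, since there are several miR-1 and primary-transcript outcomes.

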Figure 10. Human exosomal miR-1 abundance following a bout of resistance exercise. Subjects performed a bout of resistance exercise (knee extension) to failure. Blood was collected pre- and post-exercise (0, 30, 60 and 90 minutes) followed by immediate isolation of exosomes from plasma and qPCR analysis of exosomal miR-1 abundance. Following resistance exercise, exosomal miR-1 abundance was trending higher after 30 and 60 minutes post-exercise, returning to baseline by 90 min. Data are presented as mean +/- SEM (n = 10).

used miR-1 as a readout of muscle-derived exosomes. To more rigorously test our working hypothesis that skeletal muscle-derived exosomes alter adipose metabolism, we have developed an *in vitro* model of RE using human myotubes. As shown in Fig. 9A-B, electrical stimulation of human myotubes appeared to increase myotube size compared to unstimulated myotubes and, importantly, resulted in a 5-fold increase in the abundance of miR-1 in exosomes isolated from the culture media (Fig. 9C). Moreover, there was a small decrease (9%) in myotube miR-1 expression with electrical stimulation (Fig. 9D). Although we were unable to run statistics because of insufficient “n” (n=2), the overall trend in myotube size and both exosomal and myotube miR-1 abundance follows the same general pattern shown in Fig. 1 for RE.

As an initial effort to test whether or not our working model translates into humans, we carried out a pilot study. Young, sedentary, adults (n=10, 5 females, 5 males) performed a bout of RE (knee extension) to failure. Blood was collected pre- and post-exercise (0, 30, 60 and 90 minutes). Exosomes were isolated from serum and miR-1 abundance quantified by qPCR. Thirty minutes

post-exercise there was a trend for an increase in exosomal miR-1 abundance. This result suggests that both mice and humans respond to RE in a similar manner by releasing miR-1 into the circulation through exosomes. Further, this pilot demonstrates we have the necessary expertise and infrastructure to successfully conduct the human RE study proposed in Aim 3.

Collectively, we have provided strong preliminary data to support a novel mechanism in which skeletal muscle, in response to RE, regulates adipose metabolism through the exosomal delivery of muscle-specific miR-1. Also, our preliminary data clearly demonstrate that we have both intellectual and technical expertise to successfully perform the proposed experiments.

APPROACH

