Expected outcomes and alternative approaches. We expect that the bout of lower extremity RE will result in decreased miR-1 abundance in muscle at 60 minutes, a rapid and transient increase in exosomal miR-1, and a subsequent increase in adipose miR-1 abundance at 90 minutes. We do not anticipate changes in miR-1 primary transcript abundance in adipose tissue which would support our hypothesis that miR-1 is delivered via exosomes. miR-1 is highly expressed in muscle and we acknowledge that a single bout of RE may not significantly decrease muscle miR-1 expression, even if it is packaged and released in exosomes. Moreover, 60 minutes post-exercise may not be the appropriate time point to detect this change. Our pilot time course blood sampling study following RE suggested that miR-1 in serum exosomes is highest at 30 minutes and is beginning to decrease by 1 hr post exercise. Thus, we expect delivery to adipose should be detectable at 90 minutes. We acknowledge that this time point may not enable us to capture any changes in downstream targets of miR-1, but will provide proof-of-principle for a large scale clinical exercise trial that would include additional post-exercise time points following an acute bout of RE, as well as a training component.

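### Exosomal miR-1 at five blood times: unadjusted LSD after one overall test does not control familywise error if the lean group responds and the obese group does not

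*Combined protocol and SAP*

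**What the plan says.** In the combined protocol and SAP, the Statistical Analysis paragraph of Specific Aim 3 specifies one repeated-measures ANCOVA, adjusted for sex, to "determine if a significant difference exists between the groups in response to RE" for miR-1 and its primary transcripts. If that test is significant, "LSD *post-hoc* comparisons will be performed to identify the source of significance", at 0.05. The paragraph gives no multiplicity adjustment and no list of comparisons. It does not name the model term that must be significant first, although its wording points to group-by-time.

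The Aim 3 design has "blood samples drawn pre- and immediately, 30, 60 and 90 minutes post-exercise", so exosomal miR-1 has five times. Muscle and adipose miR-1 have one sample before and one after exercise.

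The section on expected outcomes of Aim 3 anticipates "a rapid and transient increase in exosomal miR-1". It states the purpose of the two groups: "Including both lean and obese individuals will determine if adiposity affects the miR-1 acute response to RE". It also says: "It is possible that release of miR-1 in exosomes from muscle will be lost or blunted in the obese cohort". In the pilot (Preliminary Data, Figure 10), "exosomal miR-1 abundance was trending higher after 30 and 60 minutes post-exercise, returning to baseline by 90 min".

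**The concern.** LSD after a significant overall test protects well when nothing changes at all. With more than three means it stops protecting the remaining true nulls as soon as one real effect makes the overall test significant.

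The plan describes such a case. If the lean group responds and the obese group does not, the lean change alone produces a significant result, under either a group-by-time or a time test. All four obese post-versus-pre comparisons are then run at an unadjusted 0.05. So are the lean comparisons at times that do not truly change.

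A false obese increase could be reported as a retained response. A false lean difference would misstate how long the rise lasts. The protocol intends these results to shape a later training trial in obese people.

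**Working it through.** **Inputs from the plan.** Five times; 40 recruited and 36 evaluable per group; "an expected difference in means between 1 and 1.95 and an expected standard deviation of 0.45", that is 0.95/0.45 = 2.11 SD.

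**Assumptions.** Two-sided tests; compound symmetry with correlation 0.5 between times; lean response at 30 min only or at 30 and 60 min, and null elsewhere. A smaller effect of 0.67 SD is also used, which is what 36 per group detects with 80% power in a two-sample t test. Sex was not modelled.

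**1. The plan's own figure.** The plan states no familywise error rate. Its sample size does not follow from its inputs: 2 × (1.96 + 0.842)² / 2.11² = 3.5, so 4 per group, not 36. The dropout step does reproduce: 36/0.9 = 40. This is a separate matter and does not drive the result; with 40 per group the error is the same.

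**2. Does the overall test protect?** With the obese response lost, the overall test is significant in essentially every trial at 2.11 SD. At 0.67 SD (group-by-time test) it is significant in 83% (30 min only) or 96% (30 and 60 min).

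**3. Post versus pre within each group.** Contrasts that share the pre sample have correlation ρ = 0.5 under compound symmetry. For k true nulls,

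P(at least one false) = 1 − ∫ [Φ((1.96 − √ρ x)/√(1−ρ)) − Φ((−1.96 − √ρ x)/√(1−ρ))]^k φ(x) dx.

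This gives 15.6% for the four obese nulls and 9.1% for two lean nulls. The groups are independent, so with the overall test always significant:

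| Lean times truly null | Either group |
|---|---|
| none | 15.6% |
| one | 1 − 0.844 × 0.95 = 19.8% |
| two | 1 − 0.844 × 0.909 = 23.2% |
| three | 26.2% |

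With two lean nulls, ρ of 0.3 or 0.7 gives 25.3% or 20.3%. Simulation that includes the group-by-time test (20,000 runs per setting, lean response at one or two times) gives 22-23% at 0.67 SD and 23-26% at 2.11 SD. With a pooled within-subject error under AR(1) correlation 0.7, the rate reaches about 31%.

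**4. Direction.** The obese figure is two-sided. A false obese increase occurs in about 6-8% of simulated trials.

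**5. Other readings of the comparisons, obese response lost.**
- Lean versus obese: 9-12% for differences in change, 12-16% for differences at each time.
- All pairs of times: 28.6% in the obese group and 12.2% over the three unchanged lean times (pre, 0 and 90 min), so 1 − 0.714 × 0.878 = 37.3%.

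**6. Other states of nature, post versus pre, either group.**
- Nothing changes: about 4%.
- Equal responses: 3-4% behind a group-by-time test (up to about 6.6% if sphericity fails badly and is not corrected); 17-24% behind a time test.
- Half-size obese response behind a group-by-time test: about 10% at 0.67 SD, 17-24% at 2.11 SD.

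**7. Holm over the eight contrasts, obese response lost.** With contrast-specific standard errors the familywise error is about 3-5%. With the pooled within-subject error it is 6-7% under AR(1) 0.5 and 8-9% under AR(1) 0.7. The error term therefore has to be part of the fix.

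**The case against.** The strongest reply has four parts.

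- **The comparisons are not stated.** The aim concerns a difference between groups, so the natural follow-up is lean versus obese, where the rate is 9-16%. This stands. No single percentage can be attributed to the plan, and the rate must be given by reading. Every reading examined is nevertheless above 5% when the obese response is lost.
- **The main question is safe.** Whether adiposity affects the response is answered by the group-by-time term, and LSD does not alter that test. This also stands. A reader might infer that the adiposity conclusion itself is wrong in about a quarter of trials. The documents do not support that: the 16-26% counts false findings in either direction, in both groups, including lean differences at unchanged times.
- **A lost response is only a possibility.** The same section hypothesizes that insulin sensitivity correlates with the miR-1 excursion in both populations. With equal responses behind a group-by-time test there is nothing material to correct, and there Holm does not lower the error. True, but the case is the protocol's own and is why the two groups are compared.
- **This is proof-of-principle work.** How strict familywise control should be is partly judgement. That bears on priority. It does not justify leaving the comparisons and the deciding term unspecified.

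**Conclusion.** The point holds for exosomal miR-1, conditional on a real lean response and a lost obese response. Familywise error is then about 16-26% for post versus pre within both groups, about 9-16% for lean versus obese, and about 37% for all pairs of times. A false obese increase occurs in about 6-8% of trials.

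The figures rest on assumed correlations, two-sided tests and a lean group that is null at the non-responding times. The first range rises to about 31% with a pooled error under AR(1) 0.7.

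It would be wrong to conclude that LSD inflates error everywhere in Aim 3. Each single comparison stays at 5%, the group-by-time test is unaffected, and equal responses behind a group-by-time test give no material inflation. Muscle and adipose miR-1, with two times each, are not affected over time. This is a cheap improvement, not a flaw that invalidates the analysis.

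**What to change.** In the Aim 3 Statistical Analysis paragraph:

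1. State that the group-by-time term answers whether adiposity affects the response.
2. For exosomal miR-1, replace LSD with eight pre-specified post-versus-pre contrasts (four times in each of two groups), adjusted by Holm over all eight and not conditional on an overall test.
3. Test each contrast with its own standard error, for example from paired changes or an unstructured covariance, not the pooled within-subject error. Report each with a 95% confidence interval.
4. If lean-minus-obese differences in change are also tested, do so only after a significant group-by-time test, with Holm over the four, labelled as a separate family.

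**Cost.** A few sentences and no new data. Lean 30-minute power at the plan's own 2.1 SD stays at 100%. For smaller effects, which the plan does not assume, power falls (correlation 0.5 assumed). At 0.67 SD it is about 86-87%, against 97-98% with LSD behind a time test when both groups respond. At 0.5 SD it is about 55-57%, against 83-84%. With two families each held at 5%, the joint error can reach about 5% + 5% = 10%, and the plan should say so.
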